### **Anamnesis, physical examination, and competition**

At the beginning of the study, all participants will undergo an anamnesis with a cardiovascular and otorhinolaryngological analysis to exclude the presence of cardiovascular diseases and upper airway symptoms resulting from rhinosinusitis, rhinopathies, or any other pre-existing alteration in these systems. In addition, the WURSS (Wisconsin Upper Respiratory Symptom Survey) questionnaire will be used to verify the occurrence of upper airway symptoms not only during this period but also throughout the study period (Annex 1), and the presence of premenstrual syndrome will be self-reported by the female volunteers during the anamnesis.

It is noteworthy to cite that the volunteers will be oriented to maintain their usual daily routine, including sleep, diet, and training/physical activity during the study performance. In this respect, to characterize not only the quality of life (Annex 2) but also the level of physical activity (Annex 3), questionnaires will be applied with open questions about the participants' lifestyle and habits, history and current habits of physical activity, as well as participation in competitions. Beyond these questionnaires, it will be also assessed the occurrence of discomfort or gastrointestinal problems related to the daily intake of fermented milk containing LcS or not by using a questionnaire with open questions about gastrointestinal problems will be used (Annex 4). The volunteers who reported any gastrointestinal discomfort during the ingestion of the fermented milk containing or not LcS will be oriented to immediately interrupt this ingestion and seek medical assistance. In case of the volunteer needs to interrupt the ingestion of fermented milk for five consecutive days, following medical recommendation, this volunteer and its data will be excluded from the study.

It is utmost of importance to point out that all athletes will have medical follow-ups by [name] [name], a specialist in Sports Medicine, throughout the study. Besides, through social media, all volunteers will be able to directly contact not only [name] but also other researchers involved in the study's development in order to communicate any adverse events and other unintended effects of trial interventions.

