### **LcS ingestion**

After stratification, the volunteers will be separated into two groups: (1) LcS Group (LcSG), which will ingest 1 bottle of fermented milk (80 grams) with  $40 \times 10^9$  of LcS per day; and (2) placebo/unfermented milk Group (PLG), which will consume 1 bottle of unfermented milk (80 grams), due to the absence of LcS. Both groups will begin the ingestion 30 days before the competition, maintaining it until 14 days after the competition. As previously mentioned, all volunteers will be oriented to stop drinking immediately and seek medical attention if any symptoms of gastrointestinal disturbance are perceived. To ensure the development of a double-blind study, all bottles used in the study will be kindly provided by YAKULT S/A Industria e Comércio, Brazil. The bottles will be named A and B by the company and will have the same taste, appearance, and smell. Information on the presence or absence of LcS in the bottles will be accessed only after all analyzes have been performed. In addition, to monitor the adherence of volunteers to the study's protocol, we intend not only to request the return flask fortnightly (empty or not) but also to maintain routine contact via social media with the volunteers. This contact also will allow us to provide responses and orientations to any questions by them, as well as, weekly, to perform auditing concerning the study's conduction.

It is important to clarify that the Yakult S/A Industria e Comércio, Brazil, will provide the fermented milk containing LcS and also the placebo/unfermented milk. In addition, Yakult Honsha Co., Ltd. Japan, will fund the development of the study, which includes all the materials needed to perform the collection, procedures, storage, and laboratory evaluations of

the biological samples obtained on all occasions described in the study. Besides, it is noteworthy to mention that the design, management, data check and analysis, and preparation of the reports/articles of the study are entirely under the responsibility of the researchers.

Regarding the ingestion period, it is based on the study by [name] et al. (2019), which showed a remarkable capacity of fermented milk containing LcS in modulating several immune/inflammatory parameters, both systemic and in the upper airways, in runners after a marathon.

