### **Sample collection**

Blood, saliva, and nasal swab will be collected on five different occasions: (1) before the beginning of the ingestion of fermented milk containing LcS or placebo; (2) 24 hours before the triathlon competition; (3) immediately (IM); (4) 72 hours (post-72h); and (5) 14 days after the competition, as shown in Figure 1. In addition, on the same occasions, the occurrence of upper airway symptoms and mood states will also be assessed by using questionnaires.

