In addition, the McNemar Chi-square test (with Yates correction) will be used to determine whether the difference in the number of volunteers who presented or not upper airway symptoms, as well as in the duration of the symptoms, is significantly different in each group (paired analysis). Additionally, Chi-square test will be used to perform the same analysis but between the volunteer groups (unpaired analysis).

A risk of less than to 0.05 ( $p<0.05$ ) will be considered statistically significant for every study.

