## WORK PLAN AND SCHEDULE

For the performance of the present study, we propose a work plan and schedule that will need 12 months to be developed. Thus, a scale of monitoring and collection of materials will be recommended, which initially will depend on the availability of each volunteer recruited to carry out the long-term triathlon competition.

Thus, we propose the following work plan and schedule:

- Recruitment of athletes and performance of clinical evaluations on all volunteers included in the study;
- Collection of blood, saliva, and nasal swab samples before starting the daily intake of fermented milk containing or not the bacteria (LcS group, n=35-40; Placebo group, n=35-40, respectively).

- study volunteers will ingest the fermented milk for 44 days;
- Collection of blood, saliva, and nasal swab samples 24 hours before the competition;
- realization of the competition by all volunteers included in the study;
- Collection of blood, saliva, and nasal swab samples immediately after the end of the competition;
- Collection of blood, saliva, and nasal swab samples 72 hours after the competition;
- Collection of blood, saliva, and nasal swab samples 14 days after the competition;
- Evaluation of the occurrence of upper airway symptoms throughout the study's period;
- Performing the laboratory evaluations described in the Material and Methods section; - Statistical analysis of the results and preparation of the report.

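### Upper airway symptoms are tested for change separately within each arm, over periods the plan does not name, and nothing says that only the between-arm test can support a conclusion about LcS

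*Combined protocol and SAP*

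**What the plan says.** The Secondary objective asks about the effect of LcS on the incidence and duration of upper airway symptoms before and after the competition. For these outcomes the Statistical analysis section plans two kinds of test.

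- Within each arm, "the McNemar Chi-square test (with Yates correction) will be used to determine" whether the number of volunteers with symptoms, and the duration of symptoms, "is significantly different in each group (paired analysis".
- Between arms, a "Chi-square test will be used to perform the same analysis but between the volunteer groups (unpaired analysis".

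A p value under 0.05 "will be considered statistically significant for every study". The section does not name the two states or periods that McNemar pairs, and it does not rank the tests.

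Other sections bear on what could be paired:

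- **LcS ingestion:** "Both groups will begin the ingestion 30 days before the competition, maintaining it until 14 days after the competition".
- **Sample collection:** "on the same occasions, the occurrence of upper airway symptoms and mood states will also be assessed by using questionnaires", meaning the five sampling occasions.
- **Work plan and schedule:** "Evaluation of the occurrence of upper airway symptoms throughout the study's period". The Anamnesis section also says symptoms are checked throughout.
- **Annex I:** a daily form with 24-hour recall.
- **Anamnesis:** screening is meant "to exclude the presence of cardiovascular diseases and upper airway symptoms resulting from rhinosinusitis, rhinopathies, or any other pre-existing alteration" in these systems.

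**The concern.** The objective is a contrast between LcS and placebo, but the McNemar test in one arm contains no such contrast. It asks whether athletes in that arm changed over time. The answer depends on the race, the season, how long each period lasts and who was let in, all of which act on both arms.

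The plan yields three p values for one outcome (LcS arm, placebo arm, between arms), all judged at 0.05, with no rule for the case where they disagree. A report could then state that symptoms rose significantly on placebo but not on LcS when the arms do not differ. Because the paired periods are not fixed, they could also be chosen after the data are seen.

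**Working it through.** **The plan's own figure.** The only sample-size figure is for salivary IgA: 62 in total for 85% power, with f = 0.15, 2 groups, 5 measurements, correlation 0.5 and ε = 1. The noncentrality is f²·N·m/(1−ρ) = 0.0225 × 62 × 5 / 0.5 = 13.95, with 4 and 240 degrees of freedom. Power is 0.857 at N = 62 and 0.844 at N = 60, so 62 is reproduced for equal groups. No figure is given for the symptom tests.

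**Inputs from the protocol.** There are 35-40 athletes per arm with 1:1 allocation. Alpha is 0.05 and the McNemar statistic is Yates-corrected. Intake runs for 30 days before and 14 days after the race. The only rate is about 30% illness in triathletes, with no time window.

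**Assumptions.** LcS has no effect, so both arms share the same rates. Pre and post states are independent within a person. All other event rates are assumed.

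**Method.** With b athletes symptomatic only before and c only after, the statistic is (|b − c| − 1)²/(b + c), significant above 3.84. The chance P that one arm is significant comes from exact enumeration over the number and split of discordant pairs. The chance that exactly one of two independent arms is significant is 2P(1 − P).

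**1. Equal windows, same race effect in both arms (20% before, 40% after).** The chance of symptoms only before is 0.2 × 0.6 = 0.12; only after, 0.4 × 0.8 = 0.32.

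| n per arm | P | Exactly one arm |
|---|---|---|
| 35 | 0.322 | 2 × 0.322 × 0.678 = 0.437 |
| 40 | 0.378 | 2 × 0.378 × 0.622 = 0.470 |

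**2. 30 days before paired with 14 days after, constant daily risk, no race effect.** The 30-day risk is 1 − (1 − p14)^(30/14). For p14 = 0.20 it is 0.380; for p14 = 0.30 it is 0.534.

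| p14 | n per arm | P | Exactly one arm |
|---|---|---|---|
| 0.20 | 35 | 0.264 | 0.389 |
| 0.20 | 40 | 0.310 | 0.428 |
| 0.30 | 35 | 0.390 | 0.476 |
| 0.30 | 40 | 0.457 | 0.496 |

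Practically all of these rejections are falls in symptoms, produced only by the shorter second window.

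**3. Nearly symptom-free start (b = 0).** Six new cases give (6 − 1)²/6 = 4.17, p = 0.041. Five give (5 − 1)²/5 = 3.2, p = 0.074. So P is the binomial chance of at least 6 cases.

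| Later incidence | P (n = 35; 40) | Exactly one arm (n = 35; 40) |
|---|---|---|
| 15% | 0.431; 0.567 | 0.491; 0.491 |
| 20% | 0.728; 0.839 | 0.396; 0.271 |
| 30% | 0.973; 0.991 | 0.052; 0.017 |

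**4. Reference.** With equal windows and no change (rates 20-40%), each arm rejects in 2.3-2.6% of trials, and exactly one arm does so in 4.5-5.1%. The planned between-arm chi-square, taken without continuity correction, has a type I error of 4.8-5.2% at event rates of 20-40%.

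**The case against.** The strongest reply is that the right test is already in the plan: the sentence after the McNemar test specifies a between-arm chi-square. Nowhere does the protocol say that LcS will be judged by setting two within-arm p values side by side, and describing the course of symptoms around the race is legitimate. This stands as far as it goes. But the section states no order among the tests and gives all of them the same threshold.

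Two stronger readings are tempting, and the documents do not support them.

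- **That McNemar compares 30 pre-race days with 14 post-race days.** Those lengths come from the intake schedule, not from a definition of the pairing. Visit-to-visit pairing with the same 24-hour recall is equally open, and then there is no imbalance. At an equal assumed prevalence of 5-30% at both visits, each arm would reject in 0.3-2.5% of trials and exactly one arm in 0.6-4.8%. Case 2 applies only if symptoms are followed throughout and the whole periods are paired.
- **That athletes are symptom-free at baseline by selection.** The Anamnesis section excludes symptoms arising from pre-existing conditions; it does not say every athlete with a symptom is screened out. Even with a clean baseline, at the protocol's own rate of about 30% both arms would nearly always be significant, and the split falls to 2-5%.

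Case 1 needs neither reading. The Yates correction is no part of the problem: it makes the within-arm test conservative.

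**Conclusion.** The point holds in this form: the plan attaches significance tests to within-arm change, leaves the paired periods undefined, and does not say which test supports a conclusion about LcS. With no LcS effect, exactly one arm is significant in 44-47% of trials when both arms rise from 20% to 40% over equal windows, and in 39-50% under 30- v 14-day pairing with a 14-day risk of 20-30%. From a nearly symptom-free baseline the split is 27-49% at a 15-20% incidence, but only 2-5% at 30%.

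These sizes rest on assumed event rates, on independence within a person and, in the second case, on constant daily risk. They show that a misleading split can easily arise; they do not predict this trial's result. It would not be right to say that the plan has no valid test of LcS on symptoms, because the between-arm chi-square is one. The outcome is secondary, so the matter should be settled before analysis but does not touch the salivary IgA conclusion.

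**What to change.** Change the Statistical analysis section to state that:

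1. conclusions about LcS and upper airway symptoms rest only on the between-arm comparison, reported as a risk difference with 95% CI over a named period;
2. the within-arm McNemar tests are descriptive and support no statement about LcS;
3. if they are kept, they pair equal windows named in advance, for example 14 days before with 14 days after the race, or matched visits with the same recall.

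The Yates correction can stay. The cost is wording only: the between-arm test is already planned, and neither the sample size nor the number of visits changes. The 14-day option does need symptoms recorded throughout, as the Work plan says; if they are captured only at visits, use matched visits. The price is that the report gives up claims of significant change within an arm.

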## WORK PLAN AND SCHEDULE

For the performance of the present study, we propose a work plan and schedule that will need 12 months to be developed. Thus, a scale of monitoring and collection of materials will be recommended, which initially will depend on the availability of each volunteer recruited to carry out the long-term triathlon competition.

Thus, we propose the following work plan and schedule:

- Recruitment of athletes and performance of clinical evaluations on all volunteers included in the study;
- Collection of blood, saliva, and nasal swab samples before starting the daily intake of fermented milk containing or not the bacteria (LcS group, n=35-40; Placebo group, n=35-40, respectively).

- study volunteers will ingest the fermented milk for 44 days;
- Collection of blood, saliva, and nasal swab samples 24 hours before the competition;
- realization of the competition by all volunteers included in the study;
- Collection of blood, saliva, and nasal swab samples immediately after the end of the competition;
- Collection of blood, saliva, and nasal swab samples 72 hours after the competition;
- Collection of blood, saliva, and nasal swab samples 14 days after the competition;
- Evaluation of the occurrence of upper airway symptoms throughout the study's period;
- Performing the laboratory evaluations described in the Material and Methods section; - Statistical analysis of the results and preparation of the report.

#### **SCHEDE OF ACTIVITIES TO BE DEVELOPED**

Parameters	Enrollment	Allocation	Intervention				
			Pre-Triathlon		Post-Triathlon		
Timepoint			-60d to -30d	-30d	-1d	0d	3d
Recruitment and selection of volunteers	X						
Informed consent	X						
Anamnesis, anthropometry, cardiopulmonary test	X						
Randomization		X					
Intervention: LcS/Placebo intake			X	X	X	X	X
Questionnaire - WURSS	X			X		X	X

Questionnaire - IPAQ	X			X			
Questionnaire - gastrointestinal problems	X			X		X	X
Questionnaire – SF36	X			X		X	X
Questionnaire – BRUMS	X			X		X	X
Questionnaire - Subjective Perception of Effort Scale	X				X		
Blood, saliva, nasal swab collection			X	X	X	X	X

## ANNEX II – Questionnaire SF36

### Versão Brasileira do Questionário de Qualidade de Vida -SF-36

1- Em geral você diria que sua saúde é:

Excelente	Muito Boa	Boa	Ruim	Muito Ruim
1	2	3	4	5

2- Comparada há um ano atrás, como você se classificaria sua idade em geral, agora?

Muito Melhor	Um Pouco Melhor	Quase a Mesma	Um Pouco Pior	Muito Pior
1	2	3	4	5

3- Os seguintes itens são sobre atividades que você poderia fazer atualmente durante um dia comum. Devido à sua saúde, você teria dificuldade para fazer estas atividades? Neste caso, quando?

Atividades	Sim, dificulta muito	Sim, dificulta um pouco	Não, não dificulta de modo algum
a) Atividades Rigorosas, que exigem muito esforço, tais como correr, levantar objetos pesados, participar em esportes árduos.	1	2	3
b) Atividades moderadas, tais como mover uma mesa, passar aspirador de pó, jogar bola, varrer a casa.	1	2	3
c) Levantar ou carregar mantimentos	1	2	3
d) Subir vários lances de escada	1	2	3
e) Subir um lance de escada	1	2	3
f) Curvar-se, ajoelhar-se ou dobrar-se	1	2	3
g) Andar mais de 1 quilômetro	1	2	3
h) Andar vários quarteirões	1	2	3
i) Andar um quarteirão	1	2	3
j) Tomar banho ou vestir-se	1	2	3

4- Durante as últimas 4 semanas, você teve algum dos seguintes problemas com seu trabalho ou com alguma atividade regular, como consequência de sua saúde física?

	Sim	Não
a) Você diminui a quantidade de tempo que se dedicava ao seu trabalho ou a outras atividades?	1	2
b) Realizou menos tarefas do que você gostaria?	1	2
c) Esteve limitado no seu tipo de trabalho ou a outras atividades.	1	2
d) Teve dificuldade de fazer seu trabalho ou outras atividades (p. ex. necessitou de um esforço extra).	1	2

5- Durante as últimas 4 semanas, você teve algum dos seguintes problemas com seu trabalho ou outra atividade regular diária, como consequência de algum problema emocional (como se sentir deprimido ou ansioso)?

	Sim	Não
a) Você diminui a quantidade de tempo que se dedicava ao seu trabalho ou a outras atividades?	1	2
b) Realizou menos tarefas do que você gostaria?	1	2
c) Não realizou ou fez qualquer das atividades com tanto cuidado como geralmente faz.	1	2

6- Durante as últimas 4 semanas, de que maneira sua saúde física ou problemas emocionais interferiram nas suas atividades sociais normais, em relação à família, amigos ou em grupo?

De forma nenhuma	Ligeiramente	Moderadamente	Bastante	Extremamente
1	2	3	4	5

7- Quanta dor no corpo você teve durante as últimas 4 semanas?

## CÁLCULO DOS ESCORES DO QUESTIONÁRIO DE QUALIDADE DE VIDA

Fase 1: Ponderação dos dados

Questão	Pontuação	
	Se a resposta for	Pontuação
01	1	5,0
	2	4,4
	3	3,4
	4	2,0
	5	1,0
02	Manter o mesmo valor	
03	Soma de todos os valores	
04	Soma de todos os valores	
05	Soma de todos os valores	
06	Pontuação	
	Se a resposta for	
	1	5
	2	4
	3	3
	4	2
	5	1

07	Se a resposta for 1 2 3 4 5 6	Pontuação 6,0 5,4 4,2 3,1 2,0 1,0
08	A resposta da questão 8 depende da nota da questão 7 Se 7 = 1 e se 8 = 1, o valor da questão é (6) Se 7 = 2 à 6 e se 8 = 1, o valor da questão é (5) Se 7 = 2 à 6 e se 8 = 2, o valor da questão é (4) Se 7 = 2 à 6 e se 8 = 3, o valor da questão é (3) Se 7 = 2 à 6 e se 8 = 4, o valor da questão é (2) Se 7 = 2 à 6 e se 8 = 3, o valor da questão é (1)	
	Se a questão 7 não for respondida, o escorre da questão 8 passa a ser o seguinte: Se a resposta for (1), a pontuação será (6) Se a resposta for (2), a pontuação será (4,75) Se a resposta for (3), a pontuação será (3,5) Se a resposta for (4), a pontuação será (2,25) Se a resposta for (5), a pontuação será (1,0)	
09	Nesta questão, a pontuação para os itens a, d, e ,h, deverá seguir a seguinte orientação: Se a resposta for 1, o valor será (6) Se a resposta for 2, o valor será (5) Se a resposta for 3, o valor será (4) Se a resposta for 4, o valor será (3) Se a resposta for 5, o valor será (2) Se a resposta for 6, o valor será (1) Para os demais itens (b, c,f,g, i), o valor será mantido o mesmo	
10	Considerar o mesmo valor.	
11	Nesta questão os itens deverão ser somados, porém os itens b e d deverão seguir a seguinte pontuação: Se a resposta for 1, o valor será (5) Se a resposta for 2, o valor será (4) Se a resposta for 3, o valor será (3) Se a resposta for 4, o valor será (2) Se a resposta for 5, o valor será (1)	

#### Fase 2: Cálculo do Raw Scale

Nesta fase você irá transformar o valor das questões anteriores em notas de 8 domínios que variam de 0 (zero) a 100 (cem), onde 0 = pior e 100 = melhor para cada domínio. É chamado de raw scale porque o valor final não apresenta nenhuma unidade de medida.

Domínio:

- Capacidade funcional
- Limitação por aspectos físicos
- Dor
- Estado geral de saúde
- Vitalidade
- Aspectos sociais
- Aspectos emocionais

848 **ANNEX III - Questionnaire of Physical Activity (IPAQ)**

849 NOME.....

850 Data.....

851 As perguntas a seguir referem-se à quantidade de atividade física que você realizou na semana  
852 passada.853 Para os 7 dias anteriores, por favor, considere a quantidade, o tipo e a intensidade da atividade física  
854 que realizaram. Se isso é mais ou menos do que o normal, isso deve ser refletido em suas respostas.855 Este tipo de atividade pode assumir qualquer forma e podem incluir atividades diárias normais,  
856 como caminhar até as lojas.857 Atividade física vigorosa refere-se a atividades que necessitaram de grandes esforços físicos para ser  
858 realizado/completado, além de exigir que você respires mais que o normal.859 Atividades moderadas referem-se a atividades que necessitaram de moderados esforços físicos para ser  
860 realizado/completado, além de exigir que você respires um pouco mais do que o normal.

861 Com relação a os treinos, tente classificar cada sessão inteira como vigorosa ou moderada.

862 Marque de forma adequada nas caixas fornecidas.

863 Seja o mais honesto possível.

864 1. Nos últimos 7 dias, quantos dias você participou de atividades físicas vigorosas, como levantamento de  
865 peso, atividades aeróbias, treinamento intenso, ciclismo, natação ou corrida?

866 \_\_\_\_\_ Dias - Se nenhum, responda 00 e passe para a pergunta 3

867 2. Nos dias em que você fez a **atividade física vigorosa** quanto tempo você costuma gastar fazendo isso?

868 \_\_\_\_\_ Horas \_\_\_\_\_ Minutos

869 3. Nos dias em que você fez **atividade física moderada** quanto tempo você costuma gastar fazendo isso?

870 \_\_\_\_\_ Dias - Se nenhum, responda 00 e passe para a pergunta 4

871 \_\_\_\_\_ Horas \_\_\_\_\_ Minutos

872 4. Nos últimos 7 dias, quantos dias você **caminhou por pelo menos 10 minutos** de cada vez?

873 \_\_\_\_\_ Dias - Se nenhum, responda 00 e passe para a pergunta 6

874 5. Nos dias em que você caminhou por pelo menos 10 minutos de cada vez, no total, quanto tempo  
875 você gasta andando?

876 \_\_\_\_\_ Horas \_\_\_\_\_ Minutos

877 6. Quanto tempo você gasta sentado em um dia normal? Pode incluir o tempo de estudo, visitando846  
 878 amigos, lendo ou assistindo televisão.  
 879 \_\_\_\_\_ Horas \_\_\_\_\_ Minutos

880 **ANNEX IV - Questionnaire gastrointestinal problems**

881 Nome.....Data.....

882 .

883 Durante a semana passada você se sentiu incomodado por qualquer um dos seguintes sintomas abaixo  
 884 listado? Por favor, indique a sua resposta através da marcação ou preenchimento do quadrante para  
 885 cada um dos seguintes:

SINTOMA	GRAU DE DESCONFORTO						
	Nenhum	Pequeno	Leve	Moderado	Moderadamente intenso	Intenso	Muito intenso
Dor abdominal							
Dor ou desconforto no abdômen aliviado por ação do intestino							
Sensação de inchaço							
Flatulência							
Constipação							
Diarreia							
Evacuação solta							
Fezes duras							
Necessidade urgente de evacuações							
Sentindo que seu intestino não foi completamente esvaziado depois de uma evacuação							
Sentindo-se completo, pouco depois de ter iniciado uma refeição							
Sentindo-se completo, mesmo depois de ter parado de comer							
Inchaço visível do seu estômago							

886 887 1. Algum destes sintomas, já afetou sua capacidade de treinar esta semana?

888 Sim ( ) Não ( )

889 Se sim, indicar qual das seguintes situações:

890 Pequena redução do treino, conseguindo manter o mesmo nível ( )

891 Treinamento reduzido abaixo do nível normal ( )

892 Parou completamente de treinar ( )

893 2. Você já tomou qualquer medicação (mesmos em receita) nesta semana para aliviar  
 894 doenças respiratórias ou sintomas de desconforto gastrointestinal?

895        Sim ( )

896        Se sim, qual o nome da medicação///

897        .....

898        Não ( )

899        3. Você se consulta com seu médico sobre seus sintomas da doença esta semana?

900        Sim ( )

901        Se sim, você tem tomado qualquer medicação prescrita esta semana?

902        Nome da medicação

903        .....

904        Não ( )

905        4. Você fez alguma alteração na sua dieta normal esta semana?

906        Sim ( )

907        Se sim, o que mudou

908        .....

909        Não ( )

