contribute to the occurrence of fatigue, gastrointestinal (GI) problems, hyperthermia, and hyponatremia that, in conjunction, can drive to a decrease of athletes' performance during this endurance exercise session (Jeukendrup, 2011). Interestingly, it was reported that central fatigue related to the central nervous system (CNS) can be alleviated with the maintenance of glycemia through different energy sources (Nybo, 2003). Based on these pieces of information, it is possible to consider that it has been well established in the literature that performance in the triathlon competition is closely influenced by the state of oxidative stress, inflammation, and energy balance.

Beyond these aspects, it is crucial to cite that in the 80' years of the last century, Morgan (1980) popularized the use of a profile mood state (POMS) in the sports context, since he identified a close association between successful athletic performance and an "iceberg" mood profile, which combined the vigor above-average, with anger, confusion, depression, fatigue, and tension below-average. Based on these facts, a new field of research was provided, and the subsequent reports reinforced the proposal that mood state is one of the most important precompetitive predictive aspects of sports performance and could be a decisive factor in athletes' results (Beedie, PC, & AM., 2000). Recently, Lochbaum and colleagues (2021) suggested that analysis of mood state by the parameters of depression, confusion, and vigor can be useful to define athletic performance when measured prospectively.

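### The graded gastrointestinal questionnaire looks back one week and is scheduled three times during intake, so it misses about 26 of 44 intake days, including the first 22

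*Combined protocol and SAP*

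**What the plan says.** The protocol section on anamnesis, physical examination and competition gives the purpose: "it will be also assessed the occurrence of discomfort or gastrointestinal problems related to the daily intake of fermented milk containing LcS or not". The instrument is Annex IV. It lists 13 symptoms, each graded on seven levels from none to very intense, and asks whether they were bothersome in the past week ("Durante a semana passada você se sentiu incomodado por qualquer um dos seguintes sintomas"). Its further items, on training, medication, medical consultation and diet, also refer to the current week.

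In the schedule of activities, the row "Questionnaire - gastrointestinal problems" has one mark at enrolment and three marks across the intervention columns. Intake runs from 30 days before the race to 14 days after it (LcS ingestion), which the work plan gives as 44 days.

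Other channels exist. Volunteers are told to stop the product and seek medical help if they have gastrointestinal symptoms. They have medical follow-up throughout and can contact the team directly about adverse events. The team collects flasks fortnightly and keeps routine contact through social media, used "as well as, weekly, to perform auditing concerning the study's conduction". An athlete who interrupts intake for five consecutive days on medical advice is to be excluded, with the data.

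**The concern.** A questionnaire with a one-week memory sees only the week before each completion. No completion is marked between the first bottle and the day before the race, so the weeks in which athletes start a new daily product fall outside every window.

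Three things follow.

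- Early intolerance is not recorded on a graded form that can be compared between arms.
- An athlete excluded before day -1 for a gastrointestinal interruption would have no Annex IV record from the intake period. An athlete kept in under the intention-to-treat rule would complete the day -1 form, but that form looks back only to about day -8. The structured data would therefore lean towards athletes who tolerated the product.
- The day 3 window contains the race. The Introduction itself says that conditions in such events can "contribute to the occurrence of fatigue, gastrointestinal (GI) problems, hyperthermia". Symptoms reported there mix race and product.

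**Working it through.** **Inputs**

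- Recall: 7 days (Annex IV).
- Intake: 30 + 14 = 44 days, which agrees with the work plan. With the race as day 0, count days -30 to 13, which is 44 days.
- Completions during intake: days -1, 3 and 14. The available text of the schedule has lost part of its header. The intake and sample rows each carry five marks in the intervention columns, and Sample collection says "Blood, saliva, and nasal swab will be collected on five different occasions": before intake, 24 hours before the race, immediately after it, 72 hours after and 14 days after. Matching the two gives columns at days -30, -1, 0, 3 and 14. The gastrointestinal row is marked in the second, fourth and fifth.

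**Coverage**

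A form completed on day v covers days v - 7 to v - 1.

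| Form | Window | Days |
|---|---|---|
| Day -1 | -8 to -2 | 7 |
| Day 3 | -4 to 2 | 7 |
| Day 14 | 7 to 13 | 7 |

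- The first two windows share days -4 to -2 (3 days), so coverage is 7 + 7 + 7 - 3 = 18 days, and 18/44 = 41%.
- Not covered: days -30 to -9 (22 days) and days 3 to 6 (4 days). 22 + 4 = 26, and 26/44 = 59%. The opening gap alone is 22/44 = 50% of intake.
- Before the race there are 30 intake days (-30 to -1). Days -8 to -1 are covered, which is 8/30 = 27%. Day -1 is seen only through the day 3 form, which also spans the race.

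**Sensitivity**

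- Counting the day of completion in the window, using an 8-day window, or counting intake as days -29 to 14 or as 45 days gives 24 to 27 uncovered days and an opening gap of 21 to 23 days.
- Suppose the form were given at all five sampling occasions. The main convention still leaves 26 days uncovered. The day -30 form looks back before intake, and the day 0 window (-7 to -1) lies inside days already covered.
- Taking the broken header at face value puts the marks at days -30, 0 and 3 and leaves 32 to 35 days uncovered. That reading also puts intake in the column for days -60 to -30, so it is not plausible.

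**The case against.** A reader might infer that intake-related intolerance cannot be assessed at all. The documents do not support that. There is an enrolment baseline, a blinded placebo arm and 18 covered days, so a randomised comparison is possible. The other channels are also more than passive messages: routine contact, fortnightly flask return and medical follow-up are run by the team. Flask returns could show missed intake by arm during the uncovered weeks. This objection stands. Its limit is that, as described, none of these channels uses a standard graded form, and a returned flask does not give a reason.

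Tolerability is neither a primary nor a secondary objective, and the statistical section plans no specific analysis of it. That also stands, and it limits the importance of the point.

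Two further inferences go too far.

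- One is that the race biases the comparison. Both arms do the same race, so it adds noise but does not by itself favour an arm. Nothing in the documents says that race-related symptoms last into days 7 to 13.
- The other is that the gap leaves the medication exclusion unenforced. That criterion sits with the initial evaluation and reads as an entry rule. Annex IV does ask about medication, and those answers are missing for the same days. How medication is recorded during the study is a separate question.

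**Conclusion.** The point holds in limited form. The only structured, graded assessment of intake-related gastrointestinal problems misses about 26 of 44 intake days (range 24 to 27), including about the first 22 (range 21 to 23). There the plan relies on unstandardised reporting. Comparison by arm is incomplete, not impossible, and is weakest for the start of intake.

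The figures rest on reading the schedule marks as days -1, 3 and 14, on a seven-day recall and on 44 days of intake. The ethics opinion gives other intake periods: one passage ends intake on the 13th day after the race, and another states 56 days. These must be reconciled with the protocol.

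The importance is minor to moderate. Salivary IgA and the listed secondary endpoints do not depend on this questionnaire.

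**What to change.** Send Annex IV remotely, through the contact the team already keeps with volunteers, on about days -22, -15, -8 and 7, in addition to days -1, 3 and 14. The new windows are -29 to -23, -22 to -16, -15 to -9 and 0 to 6. Together with the existing ones they cover days -29 to 13, or 43 of 44. Using day -23 in place of -22 brings in the first day of intake (-30 to -24) and leaves out day -23 instead.

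State that gastrointestinal symptoms will be reported by arm, separately for the pre-race period and for the race and post-race period. Assign the day 3 form to the latter, because its window spans the race. Make the schedule columns explicit. Also correct the protocol's description of the form as open questions, since Annex IV is mainly a graded grid.

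Cost: the reply to the ethics committee gives 5 to 7 minutes per completion, so 4 x 5 = 20 to 4 x 7 = 28 minutes per athlete. No visit, staff or sample is added. The downside is more questionnaire burden. The schedule table must change, and the ethics opinion requires protocol changes to be submitted as an amendment; a notification is its route for reports and adverse events.
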